8.0 SUBJECT REGISTRATION

All subjects who meet eligibility criteria for this study and sign a consent form must be registered into Velos eResearch within 24 hours of consent by a member of the Division of Hematologic Malignancies and Cellular Therapy team. We also request an email to the study chair, [name], [contact]. The eligibility checklist must be completed and the IRB approved consent form signed before any protocol therapy may be started on the patient or donor.

9.0 TOXICITY MONITORING AND ADR REPORTING

The investigator is required by Federal Regulations to report adverse experiences (AEs) that occur through the duration of the study according to the appropriate procedures listed below. The investigator is required to notify, Duke University Health System (DUHS) Institutional Review Board (IRB) Office, and DUHS Comprehensive Cancer Center if an event is serious, unexpected, and related or possibly related to the study. All serious adverse events (SAEs) that occur up to 30 days after the last Donor Lymphocyte Infusion (DLI) will be reported. After 30 days, SAEs will be reported if thought related to treatment for the duration of the study.

Definitions: An adverse event is any new, undesirable medical experience or change of an existing condition that occurs during or after treatment, whether or not considered product-related.

A serious adverse event is any untoward medical occurrence that suggests significant hazard or side effects that result in the following:

- results in death
- is life-threatening (places the patient at immediate risk of death)
- requires or prolongs in patient hospitalization
- is disabling or incapacitating

Chemo with Adoptive Haplo DLI

- is a congenital anomaly/birth defect

Any SAE will be reported to the DUHS IRB within 24 hours.

An unexpected adverse event is any adverse event, the specificity or severity of which is not consistent with the current investigator brochure or consent form.

This study will utilize the NCI Common Toxicity Criteria for Adverse Events (CTCAE) version 4.0 to determine the severity of the reaction for adverse event reporting. Only adverse events meeting criteria Grade 3 or greater will be collected. Laboratory abnormalities will only be captured if considered clinically significant. Any reactions that are reportable (serious, unexpected and related/possibly related to the study) must be reported using the Duke University Health System (DUHS) Institutional Review Board (IRB) Office SAE form. All other side effects and toxicities will be recorded in the patient's research chart or documented on the computer record for the patient.

Specific plan in the event of microbial contamination of infused product:

Product sterility testing will include a STAT gram stain which will have to be negative prior to release for infusion. A 14 day culture will be performed by our microbiology laboratory as per FDA requirements. In addition, per the SOP of sterility testing, cultures will be maintained for 5 days in our stem cell laboratory though typically the product is infused fresh the day of collection or the following day. In the event that a culture becomes positive, the lab notifies the treating physician immediately who in turn notifies the patient and the treating staff. Subjects will be evaluated within the same day of notification of a positive culture by the treating team for any infection related incidents and treated appropriately. The evaluation will include a minimum of physical examination, vital signs and blood culture.

In the event of this occurrence, this will be considered an SAE and reported in an expedited manner as above for other serious adverse events if there is a change in the health status of the patient or requiring initiation of antimicrobials.

Investigation plan in case of cellular microbial contamination:

In the event that a product has a positive culture, all reasonable efforts will be undertaken to detect the possible source. For potential donor source, donor notification and return to clinic or primary care physician for examination if there are any signs or symptoms of infection will be recommended. Examination of the chain of custody log will occur to ensure proper transit of the product and review of the exact procedure with the laboratory technician who performed the cell selection to investigate any potential difficulties that arose (tubing malfunction, bag leakage, etc).

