2.2 Secondary Objectives

2.2.1: Evaluate incidence and severity of acute GVHD.

2.2.2: Evaluate incidence and severity of other adverse events.

2.2.3: Evaluate efficacy with respect to CR and OS.

2.2.4: Evaluate immune recovery.

2.2.5: Evaluate hematopoietic recovery.

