6.4.6 Cytokine Release Syndrome

We will measure cytokine release with DLI based on peripheral blood analysis. Blood will be taken on the day of cell infusion for both induction and consolidation 2, to be drawn before infusion and 2 days after infusion for both induction and consolidation 2 to evaluate for cytokine release syndrome with DLI. For subjects who do not receive their DLI during induction but rather following consolidation #1 and consolidation #2, blood will be drawn before infusion and 2 days after infusion to measure cytokine release. We will use about 4-8 teaspoons of blood drawn from a vein by a needle-stick or through a central line each time you have these blood tests.

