7.0 EVALUATION CRITERIA AND DEFINITIONS

1. Standardized response criteria will be used following **National Comprehensive Cancer Network (NCCN)** recommendations found on the NCCN website: www.nccn.org.
2. GVHD will be graded with standard criteria (see Appendix II). Other toxicity will be graded as per the NCI Common Terminology Criteria for Adverse Events (CTCAE) version 4.0 (see Appendix III). Grade 3-4 will be reported.
3. Unacceptable toxicity will be defined as either:
 - a. Grade III or IV aGVHD of the gut or liver or Grade IV aGVHD of the skin lasting > 7 days;

Chemo with Adoptive Haplo DLI

- b. Other grade IV CTCAE toxicity attributable to the DLI (e.g. infusion reaction, and distinct from grade IV toxicity attributable to chemotherapy) and lasting > 7 days
 - c. Treatment-related mortality (TRM), keeping in mind that anticipated mortality from standard induction chemotherapy in the elderly ranges from 11% for subjects 55-65 years-old with ECOG 0 to 50% for subjects older than 75 years with ECOG 2 [1].
4. Disease-free survival (DFS) is the time from CR to relapse or death.
5. Overall survival (OS) is the time from start of therapy to either death or the last day of follow-up for that patient.
6. Event Free Survival (EFS) is the time from start of therapy to progression of AML or relapse or death.
7. Neutrophil recovery time is defined as the first of 3 consecutive days in which the ANC is $>0.5 \times 10^9/L$
8. Platelet recovery is defined as the first of 3 consecutive days in which the platelet count is $>20 \times 10^9/L$
9. PD1/PDL1/PDL2 expression (marker of T cell exhaustion)
- 10.

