12.3 Infusion Reaction/Engraftment Syndrome

Patients may experience reactions to the infusion itself including fever, chills, skin rash, pulmonary infiltrates, diarrhea, hepatic dysfunction, renal dysfunction, or confusion. Any such reaction would be transient and we would respond by slowing the infusion as per 6.3.4. Steroids, tocilizumab, acetaminophen, and intravenous fluids may also be administered in the case of such a reaction.

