| PD1/PDL1/PDL2 expression (Research) | X | | X | At 8 weeks after last therapy | X |
| Cytokine Release Syndrome (Research) | | To be drawn before infusion and 2 days after infusion for IND1, IND2, and CON2 as applicable | | | |
| Toxicity monitoring (Grade 3-4) (Epic) | | Daily | Qo wk | Qo wk till 8 weeks after last therapy and then q 4 weeks for 12 more weeks | |
| Acute GVHD monitoring (Epic) | | Daily | Qo wk | Qo wk till 8 weeks after last therapy and then q 4 weeks for 12 more weeks | |

¹ Tests at entry are recommended to be done within 1 week before initiating therapy; however if there are no sig. change in patient's status and tests are less than 4 weeks old then they are acceptable; exceptions include bone marrow aspirate and biopsy and cardiopulmonary testing (acceptable if within 8 weeks)

² Therapy and recovery refer to the period while the patient is receiving induction (IND1 or IND2) or consolidation chemotherapy until count recovery and discharge

³ For cardiopulmonary testing, refer to section 5.1.

⁴If patient already had a bone marrow biopsy and this was not collected, ok to skip

⁵ Per investigator discretion

⁶ Count Recovery would be considered when the ANC count is >1000/uL

⁷ If any subjects do not complete all the therapies (i.e. Induction 1/2, Consolidation 1 and 2), they will be followed for survival, but do not need to complete any listed assessments

⁸Any leftover cells at q3months after completing therapy will be used to run NK Lysis, TCR sequencing, and PD1/PDL1/PDL2 expression research samples. Additional blood will not be drawn for this testing.

*Other labs may be performed/followed per institutional policy

II. DONOR SCHEDULE OF EVENTS TABLE

| Test | At Entry |
|---|----------|
| History, physical (Epic) | X |
| ABC / DIFF, Serum BUN/Cr/CA/MG/PO/AST/ALT/Bili/TP/ALB/K/NA /CL/CO3/Glu/CMV viral titre (Epic) | X |
| Serum quantitative Beta-HCG for females (Epic) | X |
| CXR (AP/lateral), EKG (12 lead) (Epic) | X |
| FACT labs* (Epic) | X |
| KIR typing (Research) | X |
| Microchimerism (Research) | |
| TCR sequencing (Research) | X |

*See appendix for standard FACT (Foundation for Accreditation of Cellular Therapy) labs. FACT labs must be drawn and final test results available within 7 days prior to infusion into the patient.

III. GVHD Grading Criteria

| GvHD | | | | | | |
|--------------------|----------------------------------|----------|--|--|-------------------------------|---|

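### Grade 1-2 DLI infusion and cytokine-release reactions have no stated route into the reported adverse-event rates

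*Combined protocol and SAP*

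**What the plan says.** Objective 2.2.2 is to "Evaluate incidence and severity of other adverse events". Section 11.2.2 implements it by calculating rates, with a one-sided 85% confidence interval, for events as Sections 7.0 and 9.0 define them.

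Three places set a severity floor:
- Section 9.0: "Only adverse events meeting criteria Grade 3 or greater will be collected". It adds: "Laboratory abnormalities will only be captured if considered clinically significant".
- Section 7.0, item 2: "Grade 3-4 will be reported".
- Appendix I, recipient schedule of events: the row reads "Toxicity monitoring (Grade 3-4) (Epic".

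Section 9.0 also says: "All other side effects and toxicities will be recorded in the patient's research chart or documented on the computer record for the patient". Section 10.1.1 makes the eCRF the primary data collection document.

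On the donor lymphocyte infusion (DLI) itself, Section 12.3 lists possible reactions, from fever and rash to pulmonary infiltrates, liver or kidney dysfunction and confusion. It continues: "Any such reaction would be transient and we would respond by slowing the infusion as per 6.3.4". Steroids and tocilizumab are among the measures it allows. Section 6.4.6 takes blood before infusion and "2 days after infusion for both induction and consolidation 2 to evaluate for cytokine release syndrome with DLI", with the same pair of draws for subjects whose infusions follow the two consolidations instead.

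**The concern.** The introduction puts safety first because the procedure is new. A Grade 3 floor is a common and sensible economy for the chemotherapy backbone, where low-grade events are frequent and already well described. The cells are the investigational product, and their milder reactions are part of what a first safety study should describe.

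Under the plan as written, a non-serious Grade 2 infusion reaction, even one treated with steroids or tocilizumab, would generally not reach the Section 11.2.2 rates. Severity, which objective 2.2.2 names, would be described only from Grade 3 upward.

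The cytokine draws are affected too. The protocol states no clinical cytokine-release grade to set beside them, and no study record of steroid or tocilizumab use. A change in cytokine level could then be hard to relate to what the patient experienced or to a drug given between the two draws.

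**Working it through.** The plan states no figure for DLI reaction rates or grades, so there is none to reproduce. The check traces where an event goes and then illustrates the possible size.

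**1. Route of a non-serious Grade 2 infusion reaction**

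| Step | Source | Result |
|---|---|---|
| Observed? | 6.4.1: daily inpatient evaluation with toxicity monitoring | Yes, while admitted |
| Collected as an adverse event? | 9.0; Appendix I | No, below Grade 3 |
| Written down? | 9.0, later sentence | Research chart or computer record |
| Moved to the eCRF? | 10.1.1, 10.1.2 | Not stated |
| In the reported rates? | 11.2.2, through 7.0 and 9.0 | Not stated; 7.0 reports Grades 3-4 |

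The two sentences in Section 9.0 do not fit together cleanly. The later one directly follows the rule on reportable reactions. It could therefore cover toxicities of every grade, or only collected events that need no expedited report. The plan does not say which.

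**2. Other routes**
- Appendix IV: as the form reads, Grade 2 text appears only for seizures and for pneumonitis/pulmonary infiltrates (the latter when steroids or diuretics are needed). Hypersensitivity, including drug fever, starts at Grade 3, and no row is named for infusion reaction or cytokine release.
- Serious adverse events (9.0): reported by seriousness, not grade, up to 30 days after the last DLI.
- GVHD (11.2.1): overall rates are monitored.
- Primary composite (7.0, 11.1): the DLI-attributable CTCAE part requires Grade IV lasting more than 7 days. It lies above the floor, so the floor removes nothing from it.
- Section 11.1 tabulates toxicity outside the composite by type and grade, but it gives no wider collection rule than Section 9.0.

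**3. What a zero count would say**

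With n = 21 evaluable subjects (11.1) and no Grade 3+ reaction, the plan's one-sided 85% upper limit is 1 − 0.15^(1/21) = 0.086, or 8.6%. It bounds the Grade 3+ rate. It would be the same whether no subject or most subjects had a Grade 1-2 reaction.

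**4. Illustration on assumed inputs**

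Let q be the proportion of subjects with any reaction and s the share of those reaching Grade 3+. Neither is in the documents. Expected subjects with a reaction = 21q; expected captured = 21qs; P(none captured) = (1 − qs)^21.

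| q | s | Expected with reaction | Expected captured | P(none captured) |
|---|---|---|---|---|
| 0.20 | 0.10 | 4.2 | 0.42 | 0.65 |
| 0.40 | 0 | 8.4 | 0 | 1.00 |
| 0.40 | 0.10 | 8.4 | 0.84 | 0.42 |
| 0.40 | 0.25 | 8.4 | 2.1 | 0.11 |
| 0.40 | 0.50 | 8.4 | 4.2 | 0.01 |
| 0.60 | 0.10 | 12.6 | 1.26 | 0.27 |
| 0.60 | 0.50 | 12.6 | 6.3 | 0.001 |

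Over q from 0.20 to 0.60 and s from 0 to 0.50, the captured rate qs runs from 0% to 0.60 × 0.50 = 30%. The shortfall depends mainly on s.

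**The case against.** A reader might infer that DLI toxicity will be reported as near zero, or that most of the expected effect is hidden. The documents do not support that. Calling a reaction transient describes how long it lasts, not its grade. A brief Grade 3 reaction is still collected, and several reactions in Section 12.3 could reach Grade 3. Near-zero capture follows only if s is assumed to be close to zero. GVHD and serious events are captured whatever the CTCAE grade, and the Appendix IV form has some Grade 2 entries.

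A reader might also infer that steroid and tocilizumab use is not collected. The eCRF fields and the correlative laboratory manual are not in the documents, so one can say only that the protocol does not state it.

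Two further arguments carry weight. The adverse-event definition in Section 9.0 has no grade floor, so the reference in Section 11.2.2 could be read more widely. That makes the text ambiguous, but it does not create a route for the data. Second, the induction DLI follows chemotherapy by about 24-48 hours (Section 6.3.1) in a single-arm trial. Low-grade fever, rash or diarrhea then overlaps with chemotherapy and infection, and the Section 6.3.4 premedication, with optional hydrocortisone, can mask a reaction. An any-grade rate would not isolate DLI toxicity. This limits how the rate may be interpreted, but it is not a reason to leave the events out of the study data.

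Finally, the floor is disclosed, so a careful report would say that no Grade 3+ reactions occurred. That is true, but such a report would still leave the milder reactions undescribed.

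**Conclusion.** The point holds in a limited form. Outside the Appendix IV Grade 2 entries, serious events and GVHD, Grade 1-2 infusion or cytokine-release reactions have no stated path into the eCRF or the Section 11.2.2 rates. The protocol also pairs no clinical cytokine-release grade or record of steroid or tocilizumab use with the cytokine draws. The reported rates for objective 2.2.2 can therefore understate low-grade DLI reactions.

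The size of the understatement cannot be derived from the documents, and the table above is illustration only. A reader might extend the point to the primary safety analysis, but the composite counts only events above the floor, and its stopping rule is unchanged. Severity is minor to moderate: a descriptive secondary objective is affected, and the remedy is cheap.

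**What to change.** Keep the Grade 3+ rule for chemotherapy toxicity. Reconcile the two sentences in Section 9.0 so that it is clear which events are study data and which stay in the chart.

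For each DLI, add one short eCRF form completed from the chart, covering the start of infusion to the 2-day cytokine draw:
- any-grade CTCAE v4.0 infusion reaction or cytokine release;
- investigator attribution: DLI, chemotherapy, infection or uncertain;
- whether the infusion was slowed;
- whether and when steroids or tocilizumab were given, with steroid premedication separated from treatment.

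In Section 11.2.2, report any-grade and Grade 3+ rates per subject with exact intervals, and per infusion descriptively. Show the pre-to-post cytokine change by grade, also descriptively.

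The cost is small. Section 6.2.3 provides for at most three infusions per subject, so 21 evaluable subjects give at most 21 × 3 = 63 short records. Treatment, endpoints and sample size do not change. The limitation to state in the plan is that low-grade events soon after chemotherapy cannot be cleanly attributed to DLI without a control arm, so the any-grade rate is descriptive.

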10.0 DATA MANAGEMENT AND DATA SAFETY MONITORING

10.1 Data Management

10.1.1 Electronic Case Report Forms (eCRFs)

The eCRF will be the primary data collection document for the study. The eCRFs will be updated in a timely manner following acquisition of new source data. Only data managers are permitted to make entries, changes, or corrections in the eCRF.

Chemo with Adoptive Haplo DLI

An audit trail will be maintained automatically by our in-house Microsoft Access database. All users of this system will complete user training, as required or appropriate per regulations.

10.1.2 Data Management Procedures and Data Verification

Users of the electronic CRF will have access based on their specific roles in the protocol. Data managers have full read/write access; all other key personnel have read only access.

All data changes are tracked by an audit trail. Basic error checking is performed to ensure that legal values and dates are entered. Data managers do a full check of all data to maintain accuracy. The ability to make data modifications is based on the user's role on the study.

10.1.3 Study Closure

Following completion of the studies, the PI will be responsible for ensuring the following activities:

- Data clarification and/or resolution
- Accounting, reconciliation, and destruction/return of used and unused study drugs
- Review of site study records for completeness
- Shipment of all remaining laboratory samples to the designated laboratories

10.2 Data Safety Monitoring

The DCI Monitoring Team will conduct monitoring visits to ensure subject safety and to ensure that the protocol is conducted, recorded, and reported in accordance with the protocol, standard operating procedures, good clinical practice, and applicable regulatory requirements. As specified in the DCI Data and Safety Monitoring Plan, the DCI Monitoring Team will conduct routine monitoring after the third subject is enrolled, followed by annual monitoring of 1-3 subjects until the study is closed to enrollment and subjects are no longer receiving study interventions that are more than minimal risk.

The Safety Oversight Committee (SOC) will perform annual reviews on findings from the DCI Monitoring Team visit and additional safety and toxicity data submitted by the Principal Investigator.

Additional monitoring may be prompted by findings from monitoring visits, unexpected frequency of serious and/or unexpected toxicities, or other concerns and may be initiated upon request of DUHS and DCI leadership, the CPC, the Safety Oversight Committee (SOC), , the Principal Investigator, the Duke Clinical Trials Quality Assurance (CTQA) office or the IRB. All study documents must be made available upon request to the DCI Monitoring Team and other authorized regulatory authorities, which may include but is not limited to the National Institute of Health, National Cancer Institute.. Every reasonable effort will be made to maintain confidentiality during study monitoring.

11.0 STUDY DESIGN AND ANALYSIS

11.1 Primary Objectives:

10.1.1 Safety: Evaluate the safety of HLA-haploidentical DLI combined with conventional induction and consolidation chemotherapy in terms of unacceptable toxicity as defined in section 7.0.

A maximum of 30 subjects will be consented for a maximum of 21 evaluable subjects accrued to this protocol over a period of 2 years. Safety will be evaluated by the number of subjects with unacceptable toxicity as defined by any of the following:

- i. Grade III or IV aGVHD of the gut or liver or Grade IV aGVHD of the skin lasting > 7 days;
- ii. Grade IV CTCAE toxicity attributable to DLI (e.g. infusion reaction, as opposed to Grade IV CTCAE toxicity from chemotherapy) and lasting >7 days
- iii. Treatment-related mortality (TRM), keeping in mind that anticipated mortality from standard induction chemotherapy in the elderly ranges from 11% for subjects 55-65 years-old with ECOG 0 to 50% for subjects older than 75 years with ECOG 2 [1].

Simon's optimal two stage design will be applied. These rules permit the study to be closed early if there is evidence that the true unacceptable toxicity rate is ≥ 0.40 . The stopping rules in the table below will also allow us to test the null hypothesis that the true toxicity rate is ≥ 0.40 against the alternative hypothesis that the true toxicity rate is ≤ 0.20 . The Type I and II error rates for this design are 0.15 and 0.2, respectively. Given that the true toxicity rate is 0.40 (0.20), the probability of stopping the trial at Stage 1 to accept the null hypothesis is 0.7 (0.16). The significance level of this design is 0.15 and the power is 0.80.

| Stage | Total Accrual | Close study/therapy if number of subjects with unacceptable toxicity is \geq |
|-------|---------------|--|
| 1 | 11 | 4 (45%) |
| 2 | 21 | 7 (33%) |

Rates of unacceptable toxicity will be calculated and monitored with the stopping rules in the table above. Toxicity in the other categories will be informally monitored and tabulated by Type and Grade, but they will not be used to determine tolerability of the procedure.

Chemo with Adoptive Haplo DLI

For purposes of toxicity monitoring, each patient will be followed for unacceptable toxicity until a toxic event occurs or until 8 weeks after last cell infusion, whichever comes first. Accrual will not be suspended while collecting data for the interim analyses. However, as soon as a boundary within a stage in the table above is crossed, the study will be closed to further accrual. This design and the above boundaries will constitute our stopping rules for safety.

11.1.2 Efficacy: Evaluate the efficacy of HLA-haploidential DLI infusion combined with conventional induction and consolidation chemotherapy in terms of donor-recipient chimerism and microchimerism.

The assessment of efficacy will be conducted after collecting data for a maximum of 21 evaluable subjects. Our primary efficacy endpoint is the 1-year DFS rate following adoptive transfer. Using the chi-square test, we will test the null hypothesis is the CR rate will be ≤ 0.20 against the true hypothesis that 1-year DFS rate is >0.45 . With 21 patients, we can test this with approximately 84% power with one-sided alpha level of 0.05. Additional efficacy endpoints include the CR rate, overall response rate (CR + partial response), OS, and count recovery. CR and overall response rates will be calculated with one-sided 90% confidence interval. DFS and OS will be estimated using the method of Kaplan and Meier. All statistical analyses will be conducted in conjunction with our co-investigator, [name]., Assistant Professor of Biostatistics and Bioinformatics.

11.1.3 Geriatric assessment: Medians and frequencies will be used to describe the baseline characteristics of participants and performance on the CGA. Overall survival and associated 95% CI will be estimated as in Aim 1 and correlated with CGA measures. Cox proportional hazards models will be fit for each CGA measure as a predictor of OS, in unadjusted models and models controlling for age, gender, and ECOG score. We also will estimate the hazard ratios in adjusted Cox regression models for continuous variables. To assess the incremental impact of cognitive and physical function variables on predicting survival, we will use Integrated Discrimination Improvement as described for survival analysis by Chambliss et al.[41] and implemented in the RiskPredictionParams SAS Macro (macro version 8, Chapel Hill, NC). The variables included in the model will be those associated with survival in our analysis and included in Kantarjian's predictive model for early mortality[42]. Internal cross-validation of the model will be assessed using 1000 bootstrap replicates implemented in the RiskPredictionParams SAS macro. Logistic regression analysis will be used to investigate relationships between baseline CGA and exploratory outcomes of 30-day mortality and CR. Competing risk modeling will be used to investigate a differential effect of impairment in CGA measures by cause of death[43].

For correlative studies, probe ID's on Affymetrix U133A gene chip have been identified for the candidate cytokines and include: IL-6 (211000,

2055207, 204864, 204863, 205945, 212196), IL-1 (39402, 205067, 10118, 208200, 201404, 216245), IL-2 (207849, 204116), TNF- α (211841, 211282, 210405, 211495, 211153, 207643, 207849), and CRP (207849, 204116). The mean value for each cytokine from the Luminex assay will allow us to identify patients with high or low levels of each cytokine, and relate them to genetic typologies. Correlations between the serum cytokine levels and mRNA gene expression level for the cytokines will be evaluated by Spearman correlation. Specifically, the range of genes will be related to the panel of cytokines. Statistical significance will be assessed controlling for Type-I error using Hochberg tests, which are less conservative relative to the more common Bonferroni corrections[44, 45]. In order to reduce the dimensionality of the problem further, in follow-up tests, we will assess if factorization of the cytokines is feasible (using Principal Components Analysis (PCA)), and, if so, the resulting components will be related to the genetic typologies. We note that skew will likely be present in the cytokine panel which can impact the factorization above. We will assess skew, and, if necessary, transform the variables individually to bring about approximate normality. All analyses will be conducted at a two-sided α -level of 0.05 using SAS statistical software, version 9.2 (SAS Institute Inc., Cary, NC). We will use Spearman's correlation to assess the relationship between the biologic markers (serum cytokines and gene expression values) and clinical markers (each domain on the CGA and ECOG PS). While this work is exploratory and it could be argued that there is no need to adjust for multiple testing we will adjust p-values by the Hochberg method to control the Type-I error rate inherent in multiple testing[46]. All statistical analyses will be conducted in conjunction with our co-investigator, [name].

11.2 Secondary Objectives:

11.2.1 Evaluate incidence and severity of acute GVHD.

In addition to monitoring the rate of grade III-IV aGVHD of the gut or liver and grade IV aGVHD of the skin as in 10.1.1, we will also monitor overall rates of GVHD. Rates will be calculated with one sided 85% confidence interval.

11.2.2 Evaluate incidence and severity of other adverse events.

We will monitor other adverse events as defined in sections 7.0 and 9.0. Rates will be calculated with one sided 85% confidence interval.

11.2.3 Evaluate efficacy with respect to disease response and survival.

Additional efficacy endpoints include response rate, DFS, EFS, and OS. The response rate will be calculated with one sided 85%

Chemo with Adoptive Haplo DLI

confidence interval. DFS, EFS, and OS will be estimated using the method of Kaplan and Meier.

11.2.4 Evaluate immune recovery.

Immune reconstitution results will be tabulated and recorded. For the evaluation of recovery of immune function post-engraftment, we will use descriptive statistics of cytokine profiles, lymphocyte and NK enumeration and flow-based assays and make patient-specific plots of immune function parameters across time. These measurements will be performed prior to induction, prior to each round of consolidation, 8 weeks after the last cycle of consolidation, and every 3 months after treatment for up to 2 years. Specifically, we will:

1. monitor leukocyte subsets using flow cytometry:
 - CD3+
 - CD4+
 - CD8+
 - regulatory (CD4+, CD25+, CD62L+)
 - cytotoxic/late memory (CD8+, CD57+, CD28-) and activated (CD8+, HLADR+) T cells
 - naïve CD4+ T cells with L-selectin expression (CD4+, CD45RA+/CD45RO-, CD62L+)
 - gamma-delta T cells
 - B cells (CD19+, CD3-, CD16-, CD56-)
 - natural killer cells (NK) (CD3-, CD16+/CD56+, CD107+)
 - natural killer T cells (NKT) (CD3+, CD16+/CD56+, CD107+),
 - plasmacytoid dendritic cells (DCs) (CD123+, CD11c-)
 - myeloid DCs (CD123-, CD11c+)
2. quantify recent thymic immigrants by the presence of TCR rearrangement excision circles (TREC) performed by real-time quantitative-PCR of DNA collected from an isolated fraction of CD31 T cells
3. perform next generation sequencing of TCR gene rearrangements to analyze diversity in the TCR repertoires produced by the rearrangements of the variable region genes.
4. in vitro assays of NK function (measure CD16 expression, intracellular CD107a degranulation and cytokine secretions of IFN γ and TNF α after 4 hour co-culture with an effector:target ratio of 2:1)
5. measure immunoglobulin levels as a function of B-cell activity and recovery

Chemo with Adoptive Haplo DLI

6. measure cytokine levels, particularly IL1, IL1-beta, IL2, IL6, IL8, IL15, IL21, IFN-gamma, TNF-alpha, TGF-beta, CRP
7. microchimerism monitoring to determine the level of donor cells (as well as the presence of any pre-existing maternal-fetal microchimerism)
8. KIR typing to determine the effect of KIR ligand mismatch
9. PD1/PDL1/PDL2 expression (marker of T cell exhaustion)

11.2.5 Evaluate hematopoietic recovery.

Time to neutrophil and platelet recovery will be reported using descriptive statistics. Time to neutrophil recovery is defined according to the Center for International Blood and Marrow Transplant Research (CIBMTR) reporting guidelines. This is defined as the date of the first of three consecutive laboratory values where the ANC $\geq 500/\mu\text{l}$. If daily laboratory values were not obtained, ANC recovery is defined as three consecutive laboratory values drawn more than a day apart as long as the ANC remains $\geq 500/\mu\text{l}$. The CIBMTR defines the time to platelet recovery as the date of the first of three consecutive laboratory values obtained on different days where the platelet count was $> 20,000/\mu\text{l}$ without transfusion.

11.3 Subgroup analysis:

Subgroup analysis will be conducted based on age (55-70 vs >70), sex, WHO classification, relationship between donor and recipient, pre-existing maternal-fetal microchimerism in mother-child pairs, presence of post-infusion donor chimerism and microchimerism, HLA mismatch, and KIR-ligand mismatch.

